Clinical Protocol

NCT#02836990

Revised: August 11, 2017

Prevena Incision Management System Versus Dermabond in the Prevention of
Groin Wound Infections in Patients Undergoing Vascular Surgery

Principal Investigator: [name]
Department of Surgery
Buffalo General Medical Center
[contact]
[contact]

Sponsor: Acelity

Clinical Protocol Acceptance

I have read this protocol and agree to adhere to the requirements. I will provide copies of this protocol and all pertinent information to the study personnel. I will discuss this material with them and ensure that they are fully informed regarding the conduct of this study, other applicable regulations, to applicable laws and the University of Buffalo Health Science Institutional Review Board (HSIRB) requirements.

Principal Investigator Signature

____/____/____
DD MM YY

Principal Investigator Printed Name

Investigational Site

Protocol Synopsis

Prevena versus Dermabond in the Prevention of Groin Wound Infections in Patients Undergoing Vascular Surgery	
Protocol Number	
Test Device	Prevena Incision Management System
Primary Objective	To evaluate the clinical efficacy and cost effectiveness of Prevena versus Dermabond in preventing groin wound infections in patients who undergo vascular surgery requiring a groin incision.
Study Design	A prospective randomized study comparing groin wound infection rates and costs of hospitalization for Prevena and Dermabond in patients who undergo vascular surgery which requires a groin incision
Eligibility Criteria	Adults 18-85 who are scheduled to undergo vascular surgery which requires a groin incision who are able to consent and are willing to comply with follow-up and are or have a responsible individual deemed able to take care of a wound.
Number of Subjects	140 patients: 70 in each arm of the study
Number of Sites	Buffalo Medical Center, Kaleida Health
Follow-up schedule	Clinical follow-up will be daily throughout hospitalization including day of discharge and within 30 days of surgery to evaluate healing of the groin incision.
Primary Safety Endpoint	Major adverse event rate at 30 days defined as: groin wound infection
Primary Effectiveness Endpoint	30 day healing of the groin wound
Secondary Effectiveness Endpoint	
 1. Cost of care including hospitalization and 30 day readmission for treatment of a groin wound. 2. Incidence of antibiotic use upon discharge for treatment of infected groin incision 3. Visiting Nurse home visits and physician office visits to assess/treat groin wound infection will also be evaluated.

Table of Contents

1.0 Introduction

1.1 Objective:

The purpose of this study is to evaluate the efficacy and cost of Prevena versus Dermabond in the prevention of groin wound infections in patient who undergo vascular surgery which requires groin incision.

1.1a Device Name:

Prevena Incision Management System by Acelity

1.1b Intended Use: Prevena Incision Management System is a negative pressure wound therapy device that maintains a closed environment over the surgical incision and removes exudate through use of negative pressure. It is intended to be used on surgical incisions that continue to drain following closure with sutures or staples to prevent infection and promote healing.

1.2 Hypothesis

Groin wound infection rates as graded per the Szilagyi score following vascular surgery will be lower in patients treated with the Prevena Incision Management System than in those treated with Dermabond. The cost of using Prevena will be lower than Dermabond due to lower groin wound infection rates, need for subsequent treatment or 30 day hospital readmission for groin wound infection.

2.0 Background

The incidence of infection in groin surgical incisions following vascular procedures ranges between 3% and 44%,¹⁻⁸ which is substantially higher than expected rates.⁹ Groin incisions are particularly susceptible to complications such as infection, dehiscence, hematomas and lymphatic leaks.⁷ In part this is due to incision location and body habitus. But additionally, use of sutures and staples creates tension points that can produce ischemia and potentially cause tissue necrosis.^{Feinstein 10} Groin wound infections in vascular patients can be devastating. Graft infection may occur, particularly when prosthetic material is used, limb loss or death may even ensue. At the very minimum, infection contributes to significant increases in length of stay and cost. Surgical site infections have been estimated to cost an additional \$20,000 per admission and increase LOS by 10 days.¹¹

The purported benefits of negative pressure systems is the ability to hold incision edges together, remove exudate and debris from the site and protect the incision from other external infectious sources; attributes which would seem particularly beneficial for groin incisions. In addition to the features common to other negative pressure systems, Prevena, offers an interface layer of polyester knit fabric that functions similar to a non-adhesive dressing and protects the skin from contact with the foam bolster while delivering negative pressure and removing fluid. Moreover, Prevena is also noted for ease of use and portability.¹²

Prevena's efficacy has not yet been widely published, particularly in vascular patients, but studies which have been completed have been favorable. A small pilot study which included only 8 patients demonstrated a benefit to Prevena, however, the study was limited due to the comparator arm combining both Dermabond and Primapore dressings. ¹³Matatov et al in a larger retrospective review of 90 vascular patients with groin incisions documented that infection rates were 5 times lower with Prevena than closure with skin adhesive (Dermabond) or absorbant dressing (Primapore) 6% vs. 30%. Costs were lower with Prevena because of decreased infection rates and need for subsequent treatment. ¹⁴ Unfortunately, this study is limited by its retrospective design, lack of randomization and reporting methods. Infection rates for Dermabond and Primapore were not reported separately, yet the efficacy of these two treatment groups could differ substantially.

Prevena use has become widespread despite the lack of data from larger randomized trials. It would be beneficial to establish its clinical and cost effectiveness in a prospective randomized trial. At our hospital, Prevena is substantially more costly than Dermabond (~\$495 versus ~\$57) but even minimal reductions in infection rates may be adequate to offset expense. It is not essential that the cost of Prevena be lower than Dermabond to support its use but rather decreased infection rates paired with comparable costs will be sufficient to demonstrate its advantage.

3.0 Inclusion and Exclusion Criteria

3.1 Inclusion Criteria

- Age 18-6
- In need of elective vascular procedure requiring \geq 8cm groin incision
- Able to provide consent
- Willing to comply with follow-up

3.2 Eligibility screening

All referrals to vascular surgeons at Buffalo General Medical Center for the vascular surgery that may potentially require a groin incision will be monitored prospectively by the nurse coordinator through review of operating room schedules, and through communication with surgeons, their scheduling staff and Vascular Surgery residents. Those who meet eligibility requirements will be approached for consent and randomized accordingly.

3.3 Exclusion Criteria

- Individuals <18 years of age
- Adults unable to consent
- Subjects unable or unwilling to take care of the groin incision, use the Prevena Wound Management System or have a designated individual who is capable
- Subjects with hypersensitivity to adhesives or Silver
- Prisoners

3.4 Inclusion of non-English speaking individuals

- Every effort will be taken to include non-English speaking individuals

4.0 Study-wide Number of Subjects

4.1 Number of Subjects

A total of 140 subjects will be recruited.

There will be 70 subjects randomized to each arm.

5.0 Study-wide recruitment methods

5.1 and 5.2 Recruitment of Subjects

All referrals to vascular surgeons at Buffalo General Hospital for vascular surgery that may require groin incision

will be monitored prospectively by the nurse coordinator through review of operating room schedules and through communication with surgeons, their scheduling staff and Vascular Surgery residents. Those who meet eligibility requirements will be approached for consent and randomized accordingly.

5.3 Advertisement

Advertisement will not be necessary for the recruitment process.

6.0 Multi-Site Research Communication

6.1 The clinical coordinator will ensure compliance in the following areas and will maintain electronic documentation of compliance.

- The most current version of the protocol, consent document and HIPAA authorization are on site and available for review
- All required approvals have been obtained at each site
- All modifications have been IRB approved and communicated to each site prior to implementation
- All data will be secured in a locked cabinet in the coordinators locked office. Electronic data will be stored on a PC in the coordinator's locked office and will be password secured. Patient data will be de-identified at the earliest possible date to prevent possible breach in confidentiality.
- The coordinator will be well versed on the protocol to ensure that investigators conduct the study appropriately
 - Noncompliance with the protocol will be reported to the PI at the site and remedied appropriately.

7.0 Study Timelines

7.1 Duration of subject's participation

Subjects will be evaluated throughout hospitalization including the day of discharge, and at 30 days (25 - 40) following surgery. This will include clinical assessment (Szilagyi Scale) of the groin incision for presence of infection, need/use of antibiotics for groin

incision infection and need for visiting nurse home visits or surgeon office visit prior to scheduled follow-up to treat infection of the groin incision randomized to treatment.

[figure not shown]
7.2 Duration of enrollment period

The expected enrollment phase is 12 months

7.3 Projected completion date

The anticipated completion date for the study enrollment, follow-up data analysis, report preparation is 05/31/17.

Figure1. Study flow Diagram from Subject Screening to Follow-up

8.0 Study Endpoints

8.1 Primary and Secondary Effectiveness Endpoints

The primary effectiveness endpoint is 30 day healing of the randomized groin incision, with any wound infection or failure to heal during that period representing an endpoint. All randomized patients will be followed out to 30 days regardless of developing an infection of the randomized groin incision

The secondary effectiveness endpoint is total hospital costs including 30 day readmission for treatment of infection of the randomized groin wound.

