9.0 Procedures Involved

9.1 Study Design

This is a prospective multicenter randomized double arm study to evaluate the prevention of groin wound infections in patients undergoing vascular surgery which requires ≥ 8 cm groin incision.

9.11 Randomization Plan:

We will employ a 1:1 randomization to either Prevena or Dermabond using a stratified blocked randomization plan with strata determined as a single incision or a bilateral incision with sequences of random block sizes of 4 or 8. Within the bilateral incision strata, one incision will be randomly chosen relative to defining a single endpoint measure, with site of incision essentially serving as a secondary substratum.

9.12 Statistical Analysis Plan Outline:

Primary Endpoint

The primary endpoint for this trial will be Szilagyi wound infection grade quantified on an ordinal scale (none, grade I: infection contained to the dermus, grade II: infection extending into the subcutaneous tissue but the arterial graft is not involved, grade III: infection of the arterial graft or native vessel underlying the incision). The primary analysis will be intent to treat and carried forth using an ordinal regression model with a stratified likelihood accounting for the primary randomization strata (incision number) and binary indicator variable for treatment arm with the primary test of treatment efficacy being the proportional odds different from 1. In the event of sparse data at the higher grades of infection (<2% at grade III), categories II and III will be combined. For the bilateral incision strata, the primary endpoint will be determined by randomly choosing a single incision as determined within the randomization scheme.

Secondary Endpoint

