The secondary endpoint will be a comparison of cost of treatment between the two arms and will be considered an exploratory analysis. We will utilize regression approaches to account for potential selection bias and censored cost endpoints. We have completed a preliminary appraisal of the additional per patient hospital costs (dispersed over the entire sample) for treating groin wound infections using the following assumptions. The associated wound infection rate for Prevena would be 6%.³ Groin wound infections for Prevena and Dermabond would require comparable care. Although lower wound severity grades have been reported for Prevena³ which could potentially decrease the complexity, duration and cost of subsequent treatment of wound infection for this group, the finding was not statistically significant.³ Therefore, we projected that treatment of groin wound infection in both groups would include an increased 10 day hospital length of stay,¹ seven days of IV antibiotics, daily CBC with or without differential and 2 cultures. We have estimated that the additional per patient cost of treating groin wounds if Prevena were used preemptively (\$935- \$1,114) would be similar to Dermabond (\$869- \$1,168) if the incidence of wound infection with Dermabond is $\leq 10\%$.

9.13 Sample size rationale:

Given $N=140=70+70$ total subjects and setting the Type I error rate = 0.05, we will have the power of 0.88 to detect a proportional odds of 4.9 different from 1. For our calculations, we assumed a probability vector for the ordinal scale (none, grade I, grade II, grade III) of (0.90, 0.08, 0.019, 0.001) for the Prevena treatment arm and (0.70, 0.16, 0.11, 0.03) for the Dermabond arm respectively. The power estimate was carried forth using 10,000 Monte Carlo simulations. This volume should be easily attainable over a 12 month period because on average 484 lower extremity revascularizations and 100 Abdominal Aortic Aneurysm Repairs are performed annually at Kaleida Health. While most of these procedures (85%) are completed by endovascular approach, access by groin cutdown is necessary in 25% of EVAR and 10% of EVI in addition to the planned open lower extremity revascularizations, which should allow for adequate numbers. SPSS 22 will be used to perform the statistical analysis.

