9.6 Data/Long term Follow-up

Patients will be assessed at 30 days (25 -40) following vascular surgery with groin

incision to evaluate healing.

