Procedure Related Adverse Event	AE that have a strong temporal relationship to the procedure and an alternative etiology is unlikely
Probably Procedure Related Adverse Event	AE that have a strong temporal relationship to the procedure and an alternative etiology is less likely than the potential relationship to the procedure
Probably–Not Procedure Related Adverse Event	AE that have minimal or no temporal relationship to the procedure and/or a more than likely alternative etiology
Not Procedure –Related Adverse Event	AE is due to the underlying disease state or concomitant medication or therapy and not caused by the procedure

Criteria for MAE and SAE

Serious Infection-	Grade III Sziglgyi infection of the randomized incision
Myocardial Infarction-	Per the ESC/ACC definition for acute, evolving or recent MI Typical rise and gradual fall of Troponin or more rapid rise and fall of (CK-MB) biomarkers or myocardial necrosis with at least one of the following: 
 • Ischemic symptoms • Development of pathologic Q wave on ECG • ECG changes indicative of ischemia (ST segment elevation or depression) or coronary artery intervention (ie: coronary angioplasty • Pathologic findings of an acute MI
Congestive Heart Failure-	New or worsening shortness of breath confirmed by chest x-ray findings consistent with CHF and/or requiring unscheduled dialysis or fluid restriction
Cerebrovascular Accident-	A neurologic deficit lasting more than 24 hours, or lasting less than 24 hours with a brain imaging study showing infarction.
Pulmonary Embolus-	Embolus in the pulmonary vascular documented by CT findings
Respiratory Failure-	Respiratory difficult requiring intubation
Cardio-Pulmonary Arrest-	Loss of pulse and respiration. Need for cardio-pulmonary resuscitation to prevent impending death

Interim analysis will be performed of the primary and secondary endpoints after half of the subjects are enrolled and again when all subjects are enrolled. Anova will be used to determine differences in infection rates between the two treatment arms. The PI will verbally communicate the findings to Acelyty with recommendations to continue, stop the study or make changes to the protocol if additional patients are needed to achieve statistical significance. These will be provided in writing within 4 weeks.

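### Two different primary effectiveness endpoints are named, with no order of precedence, and only one of them is sized and given a test

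*Combined protocol and SAP*

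**What the plan says.** **Healing as primary.** The synopsis gives the primary effectiveness endpoint as "30 day healing of the groin wound", without elaboration. Section 8.1 spells it out: "30 day healing of the randomized groin incision, with any wound infection or failure to heal during that period representing an endpoint". Read literally, this is a yes/no composite of infection of any grade or failure to heal.

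**Szilagyi grade as primary.** Section 9.12, repeated in 11.1, states: "The primary endpoint for this trial will be Szilagyi wound infection grade quantified on an ordinal scale". The levels are none, I, II and III. The analysis is intention-to-treat, using an ordinal regression stratified by incision number, and the primary test is whether the proportional odds differ from 1. There is also a rule for merging grades II and III when grade III is sparse.

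**Which one the rest of the plan supports.** The hypothesis in 1.2 concerns infection: "Groin wound infection rates as graded per the Szilagyi score following vascular surgery will be lower". The sample size in 9.13 (repeated in 11.2) uses Szilagyi grade probabilities only: "we will have the power of 0.88 to detect a proportional odds of 4.9 different from 1".

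**What is assessed.** Section 9.6 says the 30-day visit follows the groin "incision to evaluate healing", and the synopsis follow-up row says much the same. Section 7.1 describes the assessments in other terms: "This will include clinical assessment (Szilagyi Scale) of the groin incision for presence of infection". The clinical status evaluation in 9.2 and the schedule in Table 1 list no healing item.

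**Interim paragraph (just before section 13.0).** For looks at the primary and secondary endpoints it names another method: "Anova will be used to determine differences in infection rates between the two treatment arms".

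**The concern.** These are two outcomes, not two wordings of one. They overlap, because any infection is grade I or higher, but they part in two places:

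| Patient | Section 8.1 | Sections 9.12 and 11.1 |
|---|---|---|
| Uninfected, not healed at 30 days | Failure | None (best level) |
| Grade I versus grade III infection | Same (failure) | Different levels |

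Failure to heal has no definition, assumed rate, test or power in the text reviewed. Someone who takes 8.1 at face value would judge the trial on an outcome to which the power of 0.88 does not apply. The two definitions can also give different verdicts on the same data, so without a stated precedence the primary could be chosen once results are known.

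**Working it through.** **Inputs from the plan (9.13).** 70 per arm; type I error 0.05, taken as two-sided because the test is of odds different from 1. Probabilities for none, I, II, III are (0.90, 0.08, 0.019, 0.001) for Prevena and (0.70, 0.16, 0.11, 0.03) for Dermabond. Any infection is therefore 1 − 0.90 = 10% and 1 − 0.70 = 30%.

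**Step 1: reproduce the plan's figure.** I simulated 200,000 trials from these vectors, without the incision-number stratum. The test was the proportional-odds score test, which is the Wilcoxon rank-sum test with tie correction. Power is 0.888, or 0.887 with the plan's rule for merging grades II and III. A separate run of 10,000 trials with the likelihood-ratio test gives 0.889. The stated 0.88 is therefore confirmed, and N = 140 is sized on the Szilagyi endpoint.

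**Step 2: the 8.1 endpoint with no uninfected non-healing.** The composite is then any infection, 10% versus 30%. An uncorrected Pearson test, simulated in the same way, has power 0.862. The gap is 0.888 − 0.862, about 0.025.

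**Step 3: how many patients could be reclassified.** Expected infections: 70 × 0.10 + 70 × 0.30 = 7 + 21 = 28. Expected uninfected: 63 + 49 = 112. Each 5% of these that fail to heal is 0.05 × 112 = 5.6, about 6 patients. They move from the best level under 9.12 to failure under 8.1.

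**Step 4: the 8.1 endpoint with some uninfected non-healing.** The documents give no rate, so the rates *u* below are assumptions. Composite rate = infection rate + (1 − infection rate) × *u*. For example, with *u* = 5% in both arms: 0.10 + 0.90 × 0.05 = 0.145 and 0.30 + 0.70 × 0.05 = 0.335.

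| Assumed *u*, Prevena / Dermabond | Composite rates | Power, 8.1 | Verdicts differ | Significant on Szilagyi only | Significant on 8.1 only |
|---|---|---|---|---|---|
| 0% / 0% | 0.100 v 0.300 | 0.862 | 2.7% | 2.6% | 0.1% |
| 5% / 5% | 0.145 v 0.335 | 0.768 | 14.3% | 13.1% | 1.2% |
| 10% / 10% | 0.190 v 0.370 | 0.672 | 24.0% | 22.8% | 1.2% |
| 5% / 10% | 0.145 v 0.370 | 0.878 | 9.1% | 5.0% | 4.1% |
| 3% / 10% | 0.127 v 0.370 | 0.930 | 7.7% | 1.7% | 6.0% |
| 5% / 15% | 0.145 v 0.405 | 0.944 | 8.8% | 1.6% | 7.2% |

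Equal non-healing dilutes the contrast and lowers power. Less non-healing with Prevena can raise it above the Szilagyi figure.

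**Step 5: sample size if 8.1 governed.** For power 0.88, the pooled-variance formula is n = [1.96 √(2p̄(1 − p̄)) + 1.175 √(p₁(1 − p₁) + p₂(1 − p₂))]² / (p₁ − p₂)². For 0.10 v 0.30 this is (1.96 × 0.566 + 1.175 × 0.548)² / 0.04 = 76.8, so 77 per arm. With 5% and 10% non-healing in both arms it gives 98 and 121. Direct simulation of the Pearson test (400,000 trials) gives about 74, 96 and 120 per arm for the three cases, against the planned 70.

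**The case against.** The best defence is that only one endpoint can be run as written. Sections 9.12 and 11.1 give the Szilagyi endpoint a population, model, strata, sparse-data rule and test, and 9.13 sizes it. The title, objective and hypothesis are all about infection. Moving to healing would mean inventing a definition and a test, which would be visible. This is a good reason to keep Szilagyi grade as primary, and it makes a silent switch harder. It does not remove the conflict: the section that defines the endpoints names something else, counts failure to heal as an event separate from infection, and is not overridden anywhere.

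A second defence concerns size. On the plan's own inputs the power gap is about 0.025 and verdicts differ in 2.7% of trials; everything larger rests on assumed non-healing rates. That is correct. Disagreement nevertheless rises quickly, to about 8% of trials with only 2% non-healing in both arms. The small gap also depends on the test chosen: Fisher's exact test gives 0.81 for 10% versus 30%, against 0.862 for Pearson.

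Third, a healing item may exist on the case report form, which was not in the text reviewed, so its absence cannot be asserted. What stands is that the reviewed text never defines failure to heal.

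**Conclusion.** The concern holds. The plan names two primary effectiveness endpoints that classify the same patient differently and sets no precedence; the stated power belongs to only one of them. The direct cost on the plan's own figures is small. With assumed uninfected non-healing of 5% to 10% in both arms, power on the 8.1 endpoint is 0.77 to 0.67, and the two endpoints reach different conclusions in 14% to 24% of trials. With unequal rates favouring Prevena, 8.1 power is 0.88 to 0.94 and conclusions differ in 8% to 9%. These figures assume the plan's grade probabilities, two-sided 0.05, an uncorrected Pearson test for the composite, no stratification and no dropout. The need to correct the text does not depend on the assumed rates, because the two definitions conflict whatever the rate turns out to be.

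**What to change.** **Primary.** In the synopsis and 8.1, name one primary endpoint: ordinal Szilagyi grade of the index incision (the randomly chosen one in bilateral cases) through the 30-day visit (days 25 to 40), analysed by the 9.12 model. Say whether the worst grade over the period or the grade at the visit counts.

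**Secondary.** In 8.1, 9.12 and 11.1, list 30-day healing (infection or failure to heal) as secondary. Define failure to heal and record it at the existing 30-day visit. Compare arms with a test stratified by incision number, for example Cochran-Mantel-Haenszel, and report the difference with a 95% interval.

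**Consistency.** Make the interim paragraph use the same primary endpoint and model. When the synopsis is edited, reconcile its safety row as well: it lists groin wound infection, whereas 8.2 lists device malfunction, grade III infection or death. Otherwise the synopsis would show infection as both primary effectiveness and primary safety.

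**Timing.** This version is dated August 11, 2017, after the 05/31/17 completion date in 7.3, and the text does not say whether enrollment has begun. If it has, record the date of the choice and that it was made without knowledge of results by arm, including from any interim look.

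**Alternative.** If the sponsor prefers the 8.1 endpoint as primary, it needs a definition, an assumed rate, a test and its own sample size.

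**Cost.** Wording amendments, a definition of failure to heal, and possibly one item in the 9.2 assessments, Table 1 and the case report form. No extra patients or visits. Healing loses its primary label.
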